EUS-guided tissue acquisition of pancreatic masses is the main modality for the diagnosis of pancreatic solid tumors including adenocarcinoma and neuroendocrine tumor. Traditionally, this is done through sampling with fine needle aspiration (FNA); however, this approach has led to variable diagnostic yield with approximately 20% of the samples being non-diagnostic¹⁻³ needing repeat procedures. Several tertiary centers worldwide have adopted rapid on-site evaluation (ROSE) of cytopathology, where a cytopathologist is at the bedside of the procedure and looking at each samples in real-time to give feedback to the endoscopists in terms of adequacy and preliminary diagnosis of their EUS-guided FNA. ROSE has been shown to increase the diagnostic yield by 10 to 15%¹ ⁴. Although currently unavailable at most Canadian sites, hospitals have been contemplating the implementation of ROSE in hopes of improving care for patients with pancreatic cancer and to prevent the need for repeat procedures and its associated costs and potential adverse events. Recently, however, novel core biopsy needles have been developed for fine needle biopsy (FNB) and histological assessment⁵. These needles allow for the acquisition of core samples with intact tissue architecture enabling immunohistochemical staining thereby enhancing the diagnostic yield. Although some studies suggest that FNB alone may be just as effective as FNA with ROSE, there are no comparative outcomes trials. As such, the goal of our study is to compare EUS-FNB with core needle sampling alone vs. EUS-FNA with ROSE in pancreatic solid lesions. If shown to be equivalent, FNB could potentially obviate the need for ROSE and be implemented in a more readily and affordable fashion across Canada.

Objectives:

Aim: To compare the diagnostic accuracy of EUS-FNB alone vs. EUS-FNA with ROSE in patients with solid pancreatic masses suspected to be of malignant origin.

Hypothesis: EUS-FNB is non-inferior to EUS-FNA with ROSE in the diagnostic accuracy for solid pancreatic masses while being associated with fewer needle passes and shorter procedure time.

Primary outcomes

- Diagnostic accuracy defined as (true positive + true negative)/all samples
- Final diagnosis will be based on the following criteria
- A) Final diagnosis of malignancy (one of the following):
 - histological evidence of malignancy on the corresponding subsequent surgical specimen
 - presence of an unresectable lesion during subsequent surgery

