 - malignant cytology/pathology on EUS-sampling followed by documented locoregional progression/development of metastases on follow-up axial imaging.
- B) Final diagnosis of benign pancreatic mass (one of the following):
 - surgical pathology or exploration showing the absence of malignancy

- follow-up imaging at > 6 months reporting stability of the pancreatic lesion
- cytological or histopathological diagnosis of benign disease with an appropriate clinical course of disease for minimum of 6 months

Secondary Outcomes

- Diagnostic characteristics: sensitivity, specificity, positive and negative predictive value
- Specimen adequacy: defined as the proportion of samples in which a final histopathological diagnosis could be made
- Median number of needle passes, procedural time
- Rate of procedure-related adverse events with severity graded as per the ASGE lexicon⁶
- Cost-effectiveness

Methods:

EUS procedure:

Procedures are performed with a linear echoendoscope under conscious sedation. EUS-FNB is performed with a 22 gauge Core-needle. Tissue sampling technique is standardized between the endoscopists. Two passes are performed using the core needle. The biopsied samples are then expressed using a stylet into a jar filled with 10% formalin. A third pass is allowed if, on macroscopic inspection of the acquired sample, the specimen is deemed insufficient by the endoscopist. EUS-FNA with ROSE is performed with a 22 gauge FNA needle. The sampled specimen is expressed into a glass slide with a stylet; then using another glass slide the sample is spread out to make smears on two slides. Each pair of slides is then numbered according to their respective needle passes. One slide is air dried and stained with modified Giemsa stain for ROSE, while the other slide is fixed in 95% ethanol and later coated with with Pananicolaou stain.

This is a multi-center, randomized, single blinded, non-inferiority, trial comparing EUS-FNB alone to EUS-FNA with ROSE in the diagnosis of solid pancreatic masses. Following consent, patients are randomized, at the time of the procedure, to undergo either EUS-FNB alone or EUS-FNA with ROSE. The randomization sequence will be generated by a computerized randomization scheme using a block size of 10 stratified according to the endoscopist.

Inclusion Criteria:

- 1. Age > 18 years

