- 2. Patients referred for EUS evaluation of a definite solid pancreatic mass noted on CT/MRI/EUS, in which malignancy is suspected with no previous histological diagnosis

Exclusion Criteria: 1.

- 1. Age < 18 years, pregnant patients
- 2. Uncorrectable coagulopathy PT>50% of control, PTT>50 sec, or INR>1.5 and/or uncorrectable thrombocytopenia platelet count<50, 000109/L.

Feasibility: The primary analysis is a noninferiority comparison of EUS-FNB vs. EUS-FNA with ROSE in terms of diagnostic accuracy, which, according to the most recent literature, is approximately 90% for both modalities. The margin of noninferiority is set at 10% in accordance with the USFDA recommendations. To achieve a statistical power of 80% with a two-sided type I error of 5%, a total of 224 patients (112 per group) is needed. Assuming a 5% dropout rate, a final sample size of 236 (118 per group) is estimated. The study is anticipated to take 2 years to complete.

Analysis: An intention-to-treat analysis will be carried out. The noninferiority hypothesis for the primary outcome will be assessed using the Z-test with a 95% two-sided confidence interval of the difference in the diagnostic accuracy and the margin of noninferiority. Interim analysis is planned after 50% of the cohort is recruited. If a > 20% difference in sensitivity is found between both methods then the study will be terminated early. Exploratory imaging and patient predictors of a diagnostic sampling is carried out using standard multivariable logistic regression analysis.

Cost-effectiveness:

A decision tree will be created for the two possible sampling approaches. Probability assumptions will be extracted from the RCT. Costs will be determined from the RAMQ. Third-party costs related to the procedure and downstream management costs will be determined based on the RCT resource utilization data. Deterministic and probabilistic sensitivity analyses will be undertaken.

Patient follow-up:

Patients will be contacted by telephone interview at 48-72 hours post procedure to ensure that no adverse events have occurred. All other follow-up will be standard of care and at the discretion of the treating physician.

Anticipated results:

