We anticipate that the results will show that EUS-FNB alone will be non-inferior to EUS-FNA with ROSE in the diagnostic accuracy of solid pancreatic masses. We also expect that both modalities will have similar diagnostic characteristics such as sensitivity, specificity, and positive and negative predictive value. Finally, the use of EUS-FNB will likely be associated with fewer needle passes, shorter procedure time, and be more cost-effective.

If our data is consistent with the anticipated results then it would have a large impact on improving diagnostic yield of EUS tissue acquisition in pancreatic mass and potentially obviate the need for on-site cytopathology at a time where centers across Canada are contemplating the addition of this effective but expensive and resource intensive modality.

MULTICENTER GUIDELINES

Protocol Chair

The Protocol Chair is responsible for performing the following tasks:

- Coordinating, developing, submitting, and obtaining approval for the protocol as well as its subsequent amendments
- Assuring that all participating institutions are using the correct version of the protocol.
- Taking responsibility for the overall conduct of the study at all participating institutions and for monitoring the progress of the study.
- Reviewing and ensuring reporting of Serious Adverse Events (SAE)
- Reviewing data from all sites

Coordinating Center

The Coordinating Center is responsible for performing the following tasks:

- Ensuring that REB approval has been obtained at each participating site prior to the first patient registration at that site, and maintaining copies of REB approvals from each site.
- Managing central patient registration.
- Collecting and compiling data from each site.
- Establishing procedures for documentation, reporting, and submitting of AE's and SAE's to the Protocol Chair, and all applicable parties.
- Facilitating audits by securing selected source documents and research records from participating sites for audit, or by auditing at participating sites.

Participating Sites

Participating sites are responsible for performing the following tasks:

- Following the protocol as written
- Submitting data to the Coordinating Center.
- Providing sufficient experienced clinical and administrative staff and adequate facilities and equipment to conduct a collaborative trial according to the protocol.
- Maintaining regulatory binders on site and providing copies of all required documents to the Coordinating Center.

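### Minor and conditional: the protocol names only intention-to-treat for the non-inferiority test, so any FNA procedure done without ROSE would weaken the comparator; a supportive as-delivered analysis is a cheap safeguard

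*Protocol*

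**What the plan says.** The Analysis paragraph states "An intention-to-treat analysis will be carried out" and continues "The noninferiority hypothesis for the primary outcome will be assessed using the Z-test with a 95% two-sided confidence interval" of the difference in accuracy, read against a 10-point margin. No per-protocol or as-treated set appears elsewhere in the protocol.

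The design paragraph under Methods says "Following consent, patients are randomized, at the time of the procedure, to undergo either EUS-FNB alone or EUS-FNA with ROSE". The comparator is therefore a package of a needle and on-site cytology. The introduction treats ROSE as the active addition: "ROSE has been shown to increase the diagnostic yield by 10 to 15" percent. It also describes ROSE as "Although currently unavailable at most Canadian sites". Under Anticipated results, the authors hope that FNB could "potentially obviate the need for on-site cytopathology".

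The only allowance for loss is in the Feasibility paragraph: "Assuming a 5% dropout rate, a final sample size of 236 (118 per group) is estimated". That is an allowance for dropout. No rate is given for FNA procedures done without ROSE.

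**The concern.** In a superiority trial, poor delivery of the treatments usually pulls an ITT comparison towards no difference, which is conservative. In a non-inferiority trial, a comparator that is delivered incompletely pulls the result towards success. Here the comparator needs a cytopathologist at the bedside and the FNB arm does not, so this delivery risk falls on one arm only.

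The intended message is that on-site cytopathology can be dispensed with. An ITT result alone cannot separate two explanations: FNB is as good as FNA with ROSE, or FNB is as good as FNA with ROSE partly missing. If ROSE delivery is not recorded, a reader of the results could not tell whether it was missed in 1% or 20% of procedures. An analysis set chosen after the data are seen would carry little weight.

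**Working it through.** **The plan's own figure.** With 90% in both arms and a 10-point margin, n per arm = (z_alpha + z_beta)² × (0.9×0.1 + 0.9×0.1) / 0.10². One-sided 5% and 80% power give (1.645 + 0.842)² × 18 = 111.3, so 112, which is the protocol's number. The stated two-sided 5% (one-sided 2.5%) gives (1.960 + 0.842)² × 18 = 141.3, so 142. That mismatch is a separate matter and the present point does not depend on it. The dropout step, 224/0.95 = 236, reproduces.

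**Inputs.** From the protocol: margin 10 points, two-sided 95% interval, 112 per arm evaluable (118 randomised), 90% accuracy for FNA with ROSE. Assumed:
- FNB is truly at the margin, 80%.
- A share d of the FNA arm lacks ROSE; d is varied.
- Accuracy falls by g without ROSE. I use g = 10 to 15 points, taking the protocol's gain in yield as a proxy for accuracy, and g = 5 points as a milder case.

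**Formula.** Under ITT the comparator's accuracy is pC = 0.90 − d×g. The chance of declaring non-inferiority is Φ[(0.80 − pC + 0.10)/SE − 1.96], with SE = √{[0.80×0.20 + pC(1 − pC)]/n}.

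**Worked case,** d = 10%, g = 10 points, n = 112: pC = 0.89; SE = √[(0.16 + 0.0979)/112] = 0.0480; 0.01/0.0480 = 0.208; Φ(0.208 − 1.96) = 4.0%.

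False non-inferiority under ITT, n = 112:

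| Missed ROSE | g = 5 points | g = 10 points | g = 15 points |
|---|---|---|---|
| 0% | 2.5% | 2.5% | 2.5% |
| 2% | 2.6% | 2.8% | 2.9% |
| 5% | 2.8% | 3.2% | 3.6% |
| 10% | 3.2% | 4.0% | 5.0% |
| 20% | 4.0% | 6.1% | 8.8% |

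At 118 per arm the figures are almost the same: for g = 10 to 15 points, 3.2 to 3.6% at 5% missed, 4.0 to 5.0% at 10% and 6.2 to 9.1% at 20%.

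**Does a supportive set help?** In a simulation at 112 per arm with Wald intervals and ROSE missed at random, ITT gives 3.6 to 4.0% at 5% missed and 4.4 to 5.4% at 10%. Limiting the FNA set to procedures with ROSE delivered gives 2.7 to 2.8% and 2.7%. With no missed ROSE the simulated ITT rate is already 2.8%, so about 0.3 of a point of each simulated excess over 2.5% comes from the interval and not from ITT.

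**If ROSE is not missed at random,** at 10% missed and g = 10 points, the supportive set gives 1.6 to 2.1% when the missed cases are harder lesions and 3.4 to 4.4% when they are easier, against 4.4% for ITT.

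**The case against.** The strongest reply is that nothing in the quoted sentence is wrong. ITT is a proper primary analysis, the sentence does not rule out others, and a supportive set with its membership rules is commonly left to a statistical analysis plan, which is not at hand. This largely stands. It is why the point is an improvement to a choice the protocol makes and not an error in it.

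The second reply is that the documents give no trigger. Patients are randomised at a single procedure, on-site staining is written into the FNA technique, sites must follow the protocol and supply adequate staff and facilities, and the risk section describes both methods as standard of care. All of this points to few missed ROSE reads, and at 2 to 5% missed the effect is small. This stands too. The 6 to 9% figures need one FNA procedure in five to lack ROSE, and nothing in the protocol supports that rate.

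A reader might infer widespread non-delivery from the remark that ROSE is "Although currently unavailable at most Canadian sites". That remark describes Canadian hospitals in general and not the participating sites.

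A reader might also infer a further bias from patients switched to another needle. The EUS procedure section provides only for a third core-needle pass when "the specimen is deemed insufficient by the endoscopist"; it mentions no switch. A switch could act in either direction, so it is no part of the case.

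What remains is the direction of the effect and the low cost of guarding against it.

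**Conclusion.** The point holds as a minor, conditional one. Missed ROSE would favour non-inferiority under the only analysis population the protocol names. The size depends on an unknown rate: with a 10 to 15 point loss, the false non-inferiority rate is about 3 to 4% if 5% of FNA procedures lack ROSE and 4 to 5% if 10% do, against 2.5%. With a 5-point loss it is 2.8% and 3.2%. These figures rest on FNB lying exactly at the margin and on yield standing in for accuracy.

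A reader might conclude that ITT is the wrong primary analysis for a non-inferiority trial, or that this trial's result will be biased. The documents support neither. A per-protocol set has its own selection bias, and no deviation rate is stated. The case for a supportive analysis is that it bears directly on the claim that on-site cytopathology is not needed.

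**What to change.** Keep ITT as the primary analysis. Record two items for each procedure: the needle used and whether ROSE was delivered. Pre-specify one supportive per-protocol analysis against the same 10-point margin, with these rules:
- The FNA set is limited to procedures in which ROSE was delivered.
- Any needle switch is handled by the same rule in both arms.
- No patient is left out because the assigned sampling failed.

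Report both results, and qualify the non-inferiority conclusion if they disagree. Do not make success in both a formal requirement: in simulation at 90% accuracy in both arms and 112 per arm, that would cut power from about 72% to 64 to 67% with 5 to 10% exclusions in each arm.

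The cost is two data items and one extra analysis that randomisation does not protect. There will also be some discordant results. With both methods truly at 90%, ITT succeeds while the supportive analysis fails in about 5 to 6% of trials at 5% missed ROSE and 9 to 11% at 10%. If an existing statistical analysis plan already contains such a set, a cross-reference in the protocol is enough.

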- Collecting and submitting data according to the schedule specified by the protocol.

ANTICIPATED RISKS

We do not anticipate major risk or discomfort beyond that associated with the conventional procedure. Both EUS-FNA with ROSE and FNB alone are part of standard or care. The following are conventional risks associated with EUS-FNA or FNB.

- 1) Perforation: Only physicians specially trained in EUS will be performing these procedures. The exact risk is minimal (<1%).
- 2) Infection: It is not standard practice to give antibiotics to all patients prophylactically for either percutaneous liver biopsy or EUS-FNA of noncystic lesions. Therefore, no subjects will receive antibiotics prophylactically for EUS sampling except those patients at risk for infective endocarditis according to American Heart Association guidelines.
- 3) Bleeding: The exact risk is minimal (1 in 5,000 chance). Doppler examination will be performed under EUS guidance prior to biopsy to ensure that the needle does not traverse a blood vessel. As a precautionary measure,

furthermore, all patients will have PTT, PT/INR, hemoglobin, and platelet count checked prior to the procedure. Those below acceptable standards will not be offered inclusion into the study. Frequent vital signs will be measured and recorded. If vital signs are abnormal and prolonged, a repeat CBC and possibly CT scan will be performed after procedure to ensure the absence of internal or external hemorrhage. These measures should ensure any clinically significant hemorrhage is detected and treated in a timely manner.

- 4) Pancreatitis (risk: 1%): Will be detected by the presence of pain with or without nausea and vomiting after pancreatic biopsy. If present, the patient will be hospitalized, kept NPO, and receive IV hydration.
- a. Steps taken to minimize the risks.
 Adherence to the standard of practice of EUS-guided tissue sampling at the McGill University Health Center as outlined above
- b. Financial risks to the participants. None.

ADVERSE EVENT REPORTING

Definition of Adverse Event (AE)

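### Randomisation is stratified by endoscopist but the primary Z-test, read plainly, uses no strata: a low-priority efficiency point, not a validity problem

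*Protocol*

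**What the plan says.** The randomisation sentence, at the end of the protocol's Methods text on the EUS procedure, generates the sequence "using a block size of 10 stratified according to the endoscopist". The Analysis paragraph then names the primary method: "The noninferiority hypothesis for the primary outcome will be assessed using the Z-test with a 95% two-sided confidence interval of the difference". The endpoint is binary (Primary outcomes: "Diagnostic accuracy defined as (true positive + true negative)/all samples"). No stratum, weight or covariate is attached to the primary comparison. The only multivariable model in that paragraph is an exploratory logistic regression on imaging and patient predictors.

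The protocol does not give the number of endoscopists, their caseloads or how far their accuracy might differ. Two statements suggest that the spread is small. Methods says "Tissue sampling technique is standardized between the endoscopists", and Anticipated Risks says "Only physicians specially trained in EUS will be performing these procedures".

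**The concern.** Blocking within endoscopist makes the arms nearly equal in each endoscopist's caseload. Differences in skill between endoscopists then largely cancel out of the comparison of arms. A plain two-proportion standard error does not know this and still counts those differences as noise. If endoscopists do differ, the interval is a little wider than the design warrants, and some power is lost for showing non-inferiority against the 10-point margin. Analysing by the factor that the trial randomises on would recover it. Naming the strata in advance also prevents a later choice between two analyses if the interval falls near the margin.

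**Working it through.** **Inputs from the protocol (Feasibility and Analysis).** Accuracy about 90% in both arms; margin 10 points; 80% power; two-sided type I error 5%, with a two-sided 95% interval; "a total of 224 patients (112 per group) is needed"; after 5% dropout, "a final sample size of 236 (118 per group) is estimated".

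**Inputs assumed, because the protocol does not give them.** 4 to 20 endoscopists, a between-endoscopist SD of accuracy from 0 to about 0.08, and even or uneven caseloads. For scale, four equal-sized endoscopists at 85, 88, 92 and 95% have SD 0.038; at 80, 87, 93 and 100% the SD is 0.074.

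**Step 1: the plan's own sample size.** Using n per group = (z₁₋α + z₀.₈₀)² × 2 × 0.9 × 0.1 / 0.10²:
- α = 0.05 one-sided: (1.645 + 0.842)² × 18 gives 112 per group.
- α = 0.025 one-sided, which is what a two-sided 95% interval implies: (1.960 + 0.842)² × 18 gives 142 per group.

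The stated 112 therefore matches the first case, not the stated 95% interval. Exact Z-test power at 90%/90% under that interval is 71.6% with 112 per group and 73.0% with 118. This is a separate matter, but it is the baseline for what follows.

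**Step 2: the standard error by formula.** With equal arms within each stratum, overall variance splits as p̄(1−p̄) = mean[pₖ(1−pₖ)] + SD². At p̄ = 0.90 the within-stratum part is 0.09 − SD². The ratio of unstratified to stratified SE is therefore √(0.09 / (0.09 − SD²)). The 95% half-width at 112 per group is 1.96 × √(2V/112), with V = 0.09 or 0.09 − SD².

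| SD | SE ratio | Half-width, unstratified | Half-width, stratified |
|---|---|---|---|
| 0 | 1.000 | 7.86 points | 7.86 points |
| 0.045 | 1.011 | 7.86 | 7.77 |
| 0.058 | 1.019 | 7.86 | 7.71 |
| 0.08 | 1.038 | 7.86 | 7.57 |

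**Step 3: power by simulation.** Patients fall to endoscopists at random. Allocation is in permuted blocks of 10 within endoscopist, with an incomplete last block, for 224 and 236 patients in total. The comparison is the Mantel-Haenszel risk difference with Sato variance against the plain Z-test, at a true difference of zero.

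| SD | Change in power, 4–10 endoscopists | Change in power, 20 endoscopists |
|---|---|---|
| 0 | −0.3 to −0.1 points | −0.7 to −0.5 |
| 0.045 | +0.5 to +0.7 | 0 to +0.2 |
| 0.058 | about +1 | +0.5 to +0.8 |

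Example with 224 patients and 6 equal strata, Z-test against stratified: 71.0% v 70.8% (no spread), 71.2% v 71.6% (SD 0.042), 71.6% v 72.6% (SD 0.058). At SD about 0.08 with 4 or 6 endoscopists the gain reaches +2.3 to +2.4 points, but nothing in the protocol suggests a spread that wide.

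**Step 4: one-sided type I error at a true difference of −10 points (nominal 2.5%).** Simulated error is 2.5% to 2.9% for the Z-test and 2.7% to 2.9% for the stratified analysis. Exact Z-test error at 80%/90% is 2.8% with either group size. The slight excess over 2.5% appears with no spread at all, so it does not come from omitting the strata.

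**The case against.** The strongest case for leaving this alone has four parts.

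- **It belongs in the SAP.** Use of stratification factors, weights and variance is commonly left to an SAP, and none is shown. The sentence does not say unstratified, and a Mantel-Haenszel difference also yields a Z statistic and a 95% interval. This stands to the extent that nothing can be called missing or contradictory. The point remains because the protocol does not leave the primary method open: it names a test that, on its plain reading, ignores the randomisation factor.
- **The simple test is defensible.** It is valid, and slightly better if endoscopists do not differ. This stands, and it is why the priority is low.
- **The size rests on assumptions.** This stands. The two statements on standardised technique and trained operators favour the smaller gains, and many small strata can turn the gain into a loss.
- **Part of the gain is bought with type I error.** At SD 0.058 the stratified error is about 2.8%, against 2.6% to 2.7% for the Z-test. With both tests held at their own simulated 2.5% critical values, the gain at SD 0.045 to 0.058 falls to about 0 to +0.5 points with 4 to 10 endoscopists. It is about zero or negative with 15 to 20 (simulation noise about 0.3). This stands too.

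A reader might infer that ignoring the strata invalidates the test or inflates false claims of non-inferiority. The calculation shows otherwise: relative to the stratified analysis the Z-test is, if anything, slightly conservative when endoscopists differ. A reader might also infer that stratifying would restore the planned 80% power. It would not.

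**Conclusion.** The point holds as an optional improvement in efficiency, with medium confidence. The design blocks on endoscopist and the named primary test, read plainly, does not use that. The cost is an interval about 1% to 2% wider than necessary if the SD between endoscopists is 0.045 to 0.058, and nothing if they do not differ. In power this is worth roughly +0.5 to +1 point with 4 to 10 endoscopists and 0 to +0.8 with 20. With no spread, stratifying loses 0.1 to 0.7 points. These figures depend on assumed numbers and spreads of endoscopists and on a mean accuracy of 90%.

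The documents do not support calling this an error, an omission or a threat to validity. Nor does it bear materially on the larger gap between the stated 80% power and the roughly 72–73% delivered under the stated 95% interval.

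**What to change.** Add to the Analysis paragraph that the primary difference in accuracy is an endoscopist-stratified Mantel-Haenszel risk difference with a Sato-type variance, and that its two-sided 95% confidence interval is compared with the 10-point margin. State a rule, set before unblinding, for pooling endoscopists with very few patients. Keep the simple Z-test as a sensitivity analysis. If an SAP already specifies strata, one aligning sentence in the protocol is enough.

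The cost is one or two sentences and no new data, since the endoscopist is known at randomisation. There are two downsides. Power falls by up to about 0.7 points if endoscopists do not differ and there are many small strata; the pooling rule limits the number of small strata. If they do differ, one-sided error is up to about 0.15 points above the Z-test's at SDs up to 0.058, and somewhat more at wider spreads. The sample-size discrepancy needs its own correction.
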